9.3.2.1 Sensitivity and Supportive Analysis of Secondary Endpoints

No sensitivity or supportive analysis is planned for the secondary endpoints.

9.3.2.2 Subgroup Analysis

Subgroup analysis of absolute change from baseline in ppFEV₁ will be performed in a manner similar to that of the primary analysis of absolute change from baseline in ppFEV₁ for the following subgroup:

- Comparator group (TEZ/IVA comparator, IVA comparator)

A similar MMRM used for the primary analysis will be used for the subgroup analysis, where the covariate of comparator group (TEZ/IVA comparator, IVA comparator) from the MMRM will be removed. The adjusted means with 2-sided 95% confidence intervals will be provided. Note that the proposed subgroup analysis will be implemented only if there are at least 20 subjects in each treatment group. Due to potential small sample size, the results from above mentioned subgroup analysis, especially the comparison between two comparator groups, should be interpreted with caution.

9.3.3 Analysis of Additional Efficacy Variables

9.3.3.1 Additional Spirometry Variables

Summary statistics for raw values and for changes from parent study baseline of the following spirometry measurements during the OL efficacy period for Part A within OL-FAS for Part A will be presented at each visit:

- FEV₁:
 - Absolute change from parent study baseline in FEV₁ (L)
 - Relative change from parent study baseline in FEV₁ (%)
 - Relative change from parent study baseline in percent predicted FEV₁ (%)
- FVC:
 - Absolute change from parent study baseline in FVC (L)
 - Relative change from parent study baseline in FVC (%)
 - Absolute change from parent study baseline in percent predicted FVC (percentage points)
 - Relative change from parent study baseline in percent predicted FVC (%)
- FEF_{25-75%}:
 - Absolute change from parent study baseline in FEF_{25-75%} (L/sec)

- Relative change from parent study baseline in FEF_{25-75%} (%)
- Absolute change from parent study baseline in percent predicted FEF_{25-75%} (percentage points)
- Relative change from parent study baseline in percent predicted FEF_{25-75%} (%)
- FEV₁/FVC:
 - Absolute change from parent study baseline in FEV₁/FVC
 - Relative change from parent study baseline in FEV₁/FVC (%)
 - Absolute change from parent study baseline in percent predicted FEV₁ / FVC
 - Relative change from parent study baseline in percent predicted FEV₁ / FVC (%)

9.4 Safety Analysis

The primary objective of the study is the evaluation of long-term safety and tolerability of TC. All safety analyses will be based on the TE Period for Part A in the OLS for subjects in the OLS for Part A. The overall long-term safety profile of study drug will be assessed in terms of the following safety and tolerability endpoints:

- Treatment-emergent adverse events (TEAEs)
- Clinical laboratory values
- ECGs
- Vital signs
- Pulse oximetry

The TC safety baseline will be used to calculate change from baseline for continuous safety endpoints.

Only descriptive analysis of safety will be performed, and no statistical testing will be performed.

9.4.1 Adverse Events

For analysis purposes, AEs will be classified as pre-treatment AEs, treatment-emergent AEs (TEAEs), or post-treatment AEs, defined as follows:

Pre-treatment AE: any AE that occurred prior to the start of the TE Period for Part A in the OLS. For subjects who enroll in another qualified Vertex study before completing this study and resume participation in this study, AEs that started during participation in another qualified Vertex study and are ongoing at the time of Returning Visit will be flagged as pre-treatment AE.

TEAE: any AE that worsened (either in severity or seriousness) or newly developed during the TE Period for Part A in the OLS

Post-treatment AE: any AE that worsened (either in severity or seriousness) or that was newly developed after the TE period for Part A in the OLS

For AEs with completely missing or partially missing start dates, if there is no clear evidence that the AEs started before or after study treatment start date in the OLS, the AEs will be

classified as TEAEs. Details for imputing missing or partial start dates of adverse events are described in Section 12.3.

An overview of all TEAEs for the OL-SS for Part A will be summarized for overall (“Any ELX/TEZ/IVA”) and include the following categories:

- Number of TEAEs (total number of TEAEs only)
- Subjects with any TEAEs
- Subjects with TEAEs by strongest relationship
- Subjects with TEAEs by maximum severity
- Subjects with TEAEs leading to study drug discontinuation
- Subjects with TEAEs leading to study drug interruption
- Subjects with Grade 3/4 TEAEs
- Subjects with related TEAEs
- Subjects with serious TEAEs
- Subjects with related serious TEAEs
- Subjects with TEAE leading to death

The frequency counts and percentages as well as the exposure adjusted event rate will be presented for the above overview table. The exposure adjusted event rate will not be presented for strongest relationship and maximum severity categories.

The following summary tables of TEAEs will be presented for overall:

- All TEAEs
- TEAEs by strongest relationship
- TEAEs by maximum severity
- Related TEAEs
- Grade 3/4 TEAEs
- TEAEs leading to treatment discontinuation
- TEAEs leading to treatment interruption
- TEAEs leading to death
- Serious TEAEs
- Related serious TEAEs

Summaries will be presented by MedDRA SOC and PT using frequency counts and percentages (i.e., number and percentage of subjects with an event). When summarizing the number and percentages of subjects, subjects with multiple occurrences of the same adverse event or a continuing adverse event will be counted once, and only the maximum severity level will be presented in the severity summaries, and the strongest relationship level in the relationship

summaries. Missing severity levels will not be included in the Grade 3/4 TEAE summaries; missing relationship will be considered as related and included in the related TEAE and related serious TEAE summaries.

Additional summary table will be presented for TEAEs overall in number and percentage of subjects.

- All TEAEs by PT

All AEs, including pre-treatment AEs, TEAEs, and post-treatment AEs, will be presented in an individual subject data listing based on the OL All Subjects Set. In addition, separate listings containing individual subject adverse event data for TEAEs leading to treatment discontinuation, TEAEs leading to treatment interruption, Grade 3/4 TEAEs, SAEs and AEs leading to death will be provided, with a flag indicating the TEAE status for SAEs and deaths.

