9.1.1 Treatment Period

Treatment Period assessments are listed in [Table 3-1](#).

Subjects will receive the first dose of study drug on Day 1 after obtaining informed consent (and assent, when applicable), confirming eligibility, and completing any pre-dose assessments. Subjects who enroll in this study on a study drug interruption will NOT receive the first dose of study drug until they meet the resumption criteria in [Section 9.8](#); before receiving study drug, subjects will repeat all Day 1 assessments.

Study drug administration details are provided in [Section 9.6](#).

The Day 1 Visit of this study should be on the same day as the last scheduled visit of the parent study.

Subjects whose Day 1 Visit is NOT within 1 day of the last scheduled visit in the Treatment Period of the parent study will have all Day 1 assessments performed.

Subjects whose Day 1 Visit is within 1 day of the last scheduled visit in the Treatment Period of the parent study will NOT have to repeat assessments that were performed as part of the last scheduled visit of the parent study Treatment Period.

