12.3.4.1 Adverse Events

For analysis purposes, AEs will be classified as pretreatment AEs, TEAEs, or post-treatment AEs, defined as follows:

- **Pretreatment AE:** any AE that occurred before the first dose of VX-445/TEZ/IVA in the TE Period in the open-label study
- **TEAE:** any AE that worsened (either in severity or seriousness) or newly developed at or after the first dose date of VX-445/TEZ/IVA in the TE Period in the open-label study
- **Post-treatment AE:** any AE that worsened (either in severity or seriousness) or newly developed after the TE Period in the open-label study

For AEs with missing or partial start dates, if there is no clear evidence that the AEs started before or after study drug treatment, then the AEs will be classified as TEAEs.

AE summary tables will be presented for TEAEs only and will include the following:

- All TEAEs
- TEAEs by strongest relationship
- TEAEs by maximum severity
- TEAEs leading to treatment discontinuation
- TEAEs leading to treatment interruption
- Serious TEAEs
- TEAEs leading to death
- Grade 3 and Grade 4 TEAEs
- Frequently reported TEAEs

Summaries will be presented by MedDRA SOC and PT using frequency counts and percentages (i.e., number and percentage of subjects with an event). When summarizing the number and percentage of subjects with an event, subjects with multiple occurrences of the same AE or a continuing AE will be counted once. Only the maximum severity level will be presented in the severity summaries, and the strongest relationship level will be presented in the relationship summaries. An AE overview table will be provided. In addition, a listing containing individual subject level AE data for all deaths and other serious and significant AEs will be provided separately. All AEs, including pre- and post-treatment AEs, will be presented in individual subject data listings.

Exposure-adjusted event rates may also be provided.

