8.2 Open Label Extension Period

OL Efficacy Period for Part A: The time from the first dose of study drug in the OLS to the last efficacy assessment, which may be collected up to the Week 96 Visit or the earlier of Day 673 and the end of study participation if subject does not have the Week 96 Visit. This analysis period will be used with the OL-FAS for Part A to analyze the efficacy data during the OLS.

OL Safety Period for Part A: The time from the first dose of study drug in the OLS to 28 days after the last dose date of the study drug in the OLS or to the completion date of study participation (defined in CSP Section 9.1.5) in Part A, whichever occurs first. This analysis period will be used with the OL-SS for Part A to analyze the safety data during the OLS.

The **Treatment-emergent (TE) Period for Part A** is same as the OL Safety Period for Part A.

Note: for subjects who depart study 110 to participate in another qualified Vertex study and return in study 110, the above defined analysis period will exclude the time between the last dose before the discontinuation from study 110 and the first dose after re-enter in study 110.

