9 STATISTICAL ANALYSIS

9.1 General Considerations

The precision standards for reporting safety and efficacy variables are provided in an internal Biometrics document that specifies the programming rules including the precision for derived variables.

Data will be summarized by treatment group in the parent study (“Control in 445-104” and “ELX/TEZ/IVA in 445-104”) and overall (“Any ELX/TEZ/IVA”).

Continuous variables will be summarized using the following descriptive summary statistics: the number of subjects (n), mean, standard deviation (SD), median, minimum value (min), and maximum value (max).

Categorical variables will be summarized using counts and percentages. Percentages will be presented to 1 decimal place.

Baseline value for clinical laboratory values, standard 12-lead ECGs, vital signs, and pulse oximetry will be the TC safety baseline defined as the most recent non-missing measurement (scheduled or unscheduled) collected before the first dose of study drug in the parent study (if the subject actually received at least one dose of ELX/TEZ/IVA during the parent study) or the first dose of study drug in the OLS (if the subject did not actually receive at least one dose of ELX/TEZ/IVA during the parent study). **Baseline value** for efficacy analyses, demographics, and baseline characteristics will be the parent study baseline defined as the most recent non missing measurement (scheduled or unscheduled) collected before the first dose of study drug in the Treatment Period of the parent study.

Change (absolute change) from baseline will be calculated as post-baseline value – baseline value. **Relative change** from baseline will be calculated as (post-baseline value – baseline value)/baseline value.

Unscheduled visits: Unscheduled visit measurements will be included in analysis as follows:

- 1) In scheduled visit windows per specified visit windowing rules
- 2) In the derivation of baseline
- 3) In the derivation of maximum and minimum values during TE period for Part A, and maximum and minimum change from baseline values during TE period for Part A for the long-term safety analyses
- 4) In individual subject data listings as appropriate

Visit windowing rules: The analysis visit windows for protocol-defined visits are provided in Section 12.1.

Incomplete/missing data will not be imputed, unless specified otherwise.

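### Adverse events carried over from triple combination in Study 104 without worsening drop out of the tables and dedicated listings of events leading to interruption or discontinuation

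*SAP*

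**What the plan says.** **Definitions.** SAP 9.4.1 defines a pre-treatment AE as "any AE that occurred prior to the start of the TE Period for Part A in the OLS" and a TEAE as "any AE that worsened (either in severity or seriousness) or newly developed during the TE Period for Part A in the OLS". SAP 8.2 equates the TE Period with the OL Safety Period: "The time from the first dose of study drug in the OLS to 28 days after the last dose date", or to completion of participation in Part A if that is sooner. Protocol 12.3.4.1 uses the same anchor. Its pretreatment class is "any AE that occurred before the first dose of VX-445/TEZ/IVA in the TE Period in the open-label study", and a TEAE must be new or worse "at or after the first dose date of VX-445/TEZ/IVA in the TE Period in the open-label study". Neither document makes an exception for subjects already on triple combination in the parent study.

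**Outputs limited to TEAEs.** Protocol 12.3.4.1 states: "AE summary tables will be presented for TEAEs only". In SAP 9.4.1 the overview rows and summary tables for discontinuation and interruption take TEAEs only, as do the separate listings for those two outcomes. The rash and transaminase summaries in SAP 9.5.1 are also limited to treatment-emergent events.

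**Outputs not limited to TEAEs.**
- SAP 9.4.1 lists all AEs by subject.
- SAP 9.4.1 also lists SAEs and AEs leading to death, with a flag for TEAE status.
- The disposition table (SAP 9.2.1) counts treatment discontinuations by reason.
- Compliance (SAP 9.2.6) counts days of interruption without their cause.

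**The concern.** Part of the cohort enters this study already on the drug. For those subjects, the first open-label dose marks a change of study, not the start of exposure. An AE that began on ELX/TEZ/IVA in Study 104, persists, and finally causes an interruption or withdrawal here is a direct observation of poor long-term tolerability, and tolerability is part of the primary objective. An action taken with study drug does not turn a pre-treatment AE into a TEAE; only worsening in severity or seriousness does. So the tables meant to show AEs that led to stopping or interrupting the drug can miss such cases. The error runs one way: the rule can remove subjects from these tables but cannot add any. The number of AE-related discontinuations in the disposition table may then exceed the number in the AE table, with nothing to explain the difference.

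**Working it through.** The plan gives no figure to reproduce here. The check is a trace through the definitions, followed by arithmetic for scale.

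**Trace for one subject**
1. The subject receives ELX/TEZ/IVA in Study 104 and has an AE with onset there. It is unresolved at the first open-label dose.
2. The TE Period starts at that dose (SAP 8.2). Onset is earlier, so the AE is pre-treatment (SAP 9.4.1; Protocol 12.3.4.1).
3. Severity and seriousness do not change in the open-label study, so the AE never becomes a TEAE.
4. Study drug is interrupted or withdrawn because of it during the OL Safety Period.
5. The event is then in neither the discontinuation or interruption tables and overview rows nor the two dedicated listings. If withdrawn, the subject is counted by reason in disposition. If interrupted, only the days appear, inside the compliance percentage.

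**Can this happen under the protocol?**
- SAP 12.3 has a rule for AEs ongoing from the parent study, so such records are expected.
- Protocol 9.1.1 foresees entry with an unresolved problem and refers to Protocol 9.8 for when dosing may start: "Subjects who enroll in this study on a study drug interruption will NOT receive the first dose of study drug until they meet the resumption" (quote cut short).
- Action without worsening is possible. In Protocol 9.8.1 one interruption criterion depends on how long ALT or AST stays above 5×ULN (more than 2 weeks), and the discontinuation rule applies even if transaminases have improved. An elevation that spans the rollover could meet either without a higher grade.
- For rash, Protocol 9.8.2 leaves resumption to the investigator. Protocol 9.9 lets the investigator withdraw a subject from treatment for safety, with no requirement that the event has worsened.

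**Scale.** Expected enrolment is about 250 (Protocol 12.1; SAP 6.2). With k subjects omitted, the table percentage is too low by 100 × k / 250:
- k = 1: 0.4 points
- k = 2: 0.8 points
- k = 5: 2.0 points

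The documents give neither the number n of subjects who had triple combination in Study 104 nor the proportion p of them with an unworsened carried-over AE that leads to interruption or withdrawal. As assumptions only, take n = 100 to 150 (40% to 60% of 250) and p = 0.5% to 4%. Expected omissions are n × p, and the chance of at least one is 1 − (1 − p)^n.

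| n | p | Expected omitted | Points of 250 | Chance of at least one |
|---|---|---|---|---|
| 100 | 0.5% | 0.5 | 0.2 | 39% |
| 125 | 1% | 1.25 | 0.5 | 72% |
| 125 | 2% | 2.5 | 1.0 | 92% |
| 150 | 4% | 6 | 2.4 | over 99% |

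**The case against.** The case against is substantial.

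**Counting TEAEs by onset within each study is legitimate.** It is prespecified, it is the same in protocol and SAP, and it avoids counting one onset in both studies. This stands, and the fix leaves the definition alone.

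**Little is wholly lost.** Discontinuations are counted by reason in disposition and every AE is in a listing. Persistent ALT or AST elevation is counted in the open-label threshold tables (SAP 9.4.2) whatever the AE onset date. This also stands, and it narrows the gap to two things: interruptions caused by such AEs, and the preferred term, severity and relatedness behind such discontinuations. The threshold tables do not show action taken with study drug.

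**The transaminase route is narrow.** Someone who enters on interruption for transaminases may resume only when an alternative reversible cause is found and values have returned to the level set in Protocol 9.8.1. A confirmed elevation without such a cause means discontinuation. A later rise would usually be a new or worsened event, hence a TEAE. What remains is an elevation that spans the rollover, and persistent events such as rash.

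**Two stronger readings are tempting but unsupported.**
- A reader might infer that the laboratory baseline contradicts the AE rule, because SAP 9.1 goes back to before the first parent-study dose "if the subject actually received at least one dose of ELX/TEZ/IVA during the parent study". That rule sets a reference value for change. It does not set the counting window: laboratory threshold events and TEAEs are both counted in the open-label TE Period.
- A reader might infer that deaths are lost too. SAP 9.4.1 already lists AEs leading to death whatever their TEAE status, and an ongoing non-serious AE that turns fatal has worsened in seriousness.

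**Unseen sources.** Whether the Study 104 outputs capture later action on these events depends on that study's SAP and on the CRF guidelines, which are not available here.

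**Conclusion.** The gap follows from the text. An AE that began on ELX/TEZ/IVA in Study 104, continues without worsening, and leads to interruption or withdrawal in the OL Safety Period is in none of the AE tables or dedicated listings for those outcomes. The direction is certain: these counts can only be too low. The size is unknown and probably small. The illustrative range of 0.5 to 6 subjects (0.2 to 2.4 points of 250) rests wholly on the assumed n and p.

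A reader might go further and infer that the main safety tables are materially biased, or that these discontinuations vanish from the report. The documents do not support the first, since no carry-over rate can be derived from them. They contradict the second, given the disposition table and the all-AE listing. The point is a low-cost improvement to the completeness of a primary tolerability outcome. It does not invalidate the planned analysis.

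**What to change.** Keep the TEAE definition and all planned TEAE tables. In SAP 9.4.1 add one summary table (by SOC and preferred term, with severity and relatedness) and one listing, for the OL-SS for Part A, of every AE that meets both conditions, whatever its TEAE status:
- the recorded action is drug interrupted or drug withdrawn; and
- the start of the interruption, or the last dose before withdrawal, falls in the OL Safety Period according to the dosing records.

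Add a flag for onset on ELX/TEZ/IVA in Study 104. This extends to interruptions and discontinuations the flagged listing that SAP 9.4.1 already uses for SAEs and deaths. Deaths need no change.

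The dosing records are needed because the AE data items in Protocol 13.1.1.3 include action taken but no date for it. Without that link, an interruption that began in Study 104 could be counted here by mistake. The compliance calculation in SAP 9.2.6 already requires interruption days, so the plan already relies on the information.

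Record the addition in SAP 2.1, which now lists no changes to the protocol, because Protocol 12.3.4.1 limits AE summary tables to TEAEs.

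The cost is an SAP amendment, the programming to link AE action with dosing dates, some case review where an interruption could belong to more than one AE, and slightly higher reported counts. No new data collection is proposed, and no clinical rule changes.

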9.4.2 Clinical Laboratory Assessments

For the treatment-emergent laboratory assessments, the observed values and change from baseline values of the continuous hematology, coagulation, and chemistry results will be summarized in SI units for overall (“Any ELX/TEZ/IVA”) at each visit during the TE period for Part A for the OLS.

The number and percentage of subjects with test values meeting at least 1 threshold analysis criterion event during the TE period for Part A for the OL-SS for Part A will be summarized for overall (“Any ELX/TEZ/IVA”). The threshold analysis criterion shift from baseline will also be summarized for selected laboratory parameters. The threshold analysis criteria are provided in Section 12.4.

Results of positive urine/serum pregnancy test will be listed in individual subject data listings only. For positive serum pregnancy listing, subjects with serum HCG which are abnormally high will be selected.

In addition, a listing containing individual subject hematology, chemistry, coagulation and urinalysis values will be provided. This listing will include data from both scheduled and unscheduled visits.

